3. STUDY OBJECTIVES

3.1. PRIMARY OBJECTIVE

The overall objective is to evaluate the safety and efficacy of teprotumumab in the treatment of Thyroid Eye Disease (TED) in subjects who participated in the lead-in study (HZNP-TEP-301) and who were either proptosis non-responders at Week 24 of HZNP-TEP-301 or were proptosis responders at Week 24 but met the criteria for re-treatment due to relapse during the Follow-Up Period of HZNP-TEP-301.

The primary objective is to evaluate the effect of teprotumumab on the proptosis responder rate (i.e., the percentage of subjects with a ≥ 2 mm reduction in proptosis from Study Baseline [see section 6.2.3] in the study eye without deterioration [≥ 2 mm increase] of proptosis in the fellow eye) at Week 24.

3.2. SECONDARY OBJECTIVES

Secondary objectives are:

1. Percentage of subjects with a Clinical Activity Score (CAS) value of 0 or 1 at Week 24 in the study eye.
2. Mean change from Study Baseline to Week 24 in proptosis measurement in the study eye.
3. Diplopia responder rate (i.e. the percentage of subjects with Study Baseline diplopia > 0 in study eye who have a reduction of ≥ 1 grade with no corresponding deterioration [≥ 1 grade worsening] in the fellow eye) at Week 24.
4. Mean change from Study Baseline to Week 24 in the Graves' Ophthalmopathy Quality of Life (GO-QoL) questionnaire overall score.

3.3. EXPLORATORY OBJECTIVES

Exploratory objectives are:

1. The overall responder rate (percentage of subjects with ≥ 2 -point reduction in CAS and ≥ 2 mm reduction in proptosis from Study Baseline, provided there is no corresponding deterioration [≥ 2 -point/mm increase] in CAS or proptosis in the fellow eye) at Week 24.
2. Clinical Measures of Severity individual response status frequencies and percentage of responders for each component of clinical severity at Week 24.
3. Mean change from Study Baseline to Week 24 in the CAS.

4. Overall responder rate at Week 24 stratified by the level of response (high responders, responders, low responders, and non-responders)
5. Mean change from Study Baseline to Week 24 in the GO-QoL questionnaire visual functioning (VF) and appearance (A) subscale scores.
6. Mean change from Study Baseline to Week 24 on the motility component of the Clinical Measures of Severity.
7. Evaluate PK parameters of teprotumumab to estimate exposure and understand PK-PD relationships.

3.4. BRIEF DESCRIPTION

This study will be conducted at up to 16 sites in the United States (US) and Europe (EU).

This is a multi-center, open-label extension study of HZNP-TEP-301 examining the safety and efficacy of teprotumumab in the treatment of TED in adult subjects. Subjects who complete the 24-week double-masked Treatment Period in Study HZNP-TEP-301 and are proptosis non-responders or were proptosis responders at Week 24 but meet the criteria for re-treatment due to relapse during the Follow-Up Period of HZNP-TEP-301 will be eligible for enrollment. The study treatment previously administered in HZNP-TEP-301 (teprotumumab or placebo) will remain masked to the [REDACTED] clinical team and study sites throughout this extension study.

All subjects who choose to participate will receive 8 infusions of teprotumumab (10 mg/kg for the first infusion followed by 20 mg/kg for the remaining 7 infusions) in an open-label fashion. The Day 1 visit of this extension study will occur within 14 days after the final visit of Study HZNP-TEP-301 (Week 24 for proptosis non-responders and up to Week 72 for subjects who relapse). During the open-label Treatment Period, study drug infusions are scheduled for Day 1 (Baseline), and Weeks 3, 6, 9, 12, 15, 18, and 21 (with a final visit at Week 24 of the 24-Week Treatment Period).

All study drug dosing will be performed at the clinic under the supervision of clinic staff. The infusion rate may be reduced or the dose may be interrupted or held based on decreased tolerability. On each dosing day, scheduled assessments (except for adverse event [AE] and concomitant medication use monitoring, which will be monitored throughout the clinic visit), will be completed prior to study drug dosing. After each of the first 2 infusions, subjects will be contacted by phone/email the following day and will return to the clinic 1 week after the infusion (Weeks 1 and 4) for safety and tolerability assessments; additional phone/email contacts and clinic visits may also be conducted for any subject experiencing an infusion-associated event.

For all the assessments, if Day 1 of the extension study occurs on the same day as the final visit of HZNP-TEP-301 (Week 24 for proptosis non-responders and Week 72 [or

Premature Withdrawal (PW)] for subjects who relapse), assessments do not need to be repeated, and the final assessments from the lead-in study will serve as the Study Baseline assessments for the extension study.

After completion of the Treatment Period, subjects who were proptosis non-responders in Study HZNP-TEP-301 will enter a 24-week Follow-Up Period, during which study drug will not be administered and clinic visits are scheduled for 1, 3, and 6 months (Visits Month 7, 9 and 12) after the Week 24 visit; if any of these subjects discontinue from the Follow-Up Period prior to the Month 12 Visit, they will return to the clinic and undergo the scheduled Month 12 assessments prior to study discharge. Those who complete the Month 12 visit will be contacted at 6 and 12 months later via phone or email by research staff to enquire if any treatment for TED has been received since last study contact. If yes, subject will be questioned regarding type of treatment and outcome/response.

Subjects who relapse during the Follow-Up Period of HZNP-TEP-301 and choose to enter this extension study will not participate in the Follow-Up Period. For these subjects, the last clinic visit is at Week 24. Those who complete the Week 24 visit will be contacted 6 and 12 months later via phone or email by research staff to enquire if any treatment for TED has been received since last study contact. If yes, subject will be questioned regarding type of treatment and outcome/response.

3.5. DETERMINATION OF SAMPLE SIZE

The sample size is not based on statistical considerations. Subjects who are proptosis non-responders at Week 24 of HZNP-TEP-301 or who are proptosis responders at Week 24 but meet the criteria for re-treatment due to relapse during the Follow-Up Period of HZNP-TEP-301 will be eligible for enrollment.

3.6. TREATMENT ASSIGNMENT & MASKING

This is an open label study. All enrolled subjects will receive 8 infusions of teprotumumab (10 mg/kg for the first infusion followed by 20 mg/kg for the remaining 7 infusions) in an open-label fashion.

Prior to the unmasking of HZNP-TEP-301, an unmasked team from [REDACTED] biostatistics performed unmasked analyses as outlined in the DSMB charter. These team members otherwise had no involvement with the study.

3.7. PREPARATION AND ADMINISTRATION OF STUDY MEDICATION

Teprotumumab 500 mg will be provided in single-dose 20 mL glass vials as a freeze-dried powder. Each vial of teprotumumab will be reconstituted with 10 mL of water for

injection. The resulting solution will have an approximate concentration of 50 mg/mL teprotumumab. Reconstituted teprotumumab solution will be further diluted in 0.9% (w/v) sodium chloride (NaCl) solution prior to administration.

Doses up to 1800 mg will be administered in a total infusion volume of 100 mL, and doses above 1800 mg will be administered in a total infusion volume of 250 mL. To maintain a constant volume in the infusion bags, a volume equal to the volume of teprotumumab to be placed into the infusion bag will be first removed from the infusion bag using a sterile syringe and needle. The appropriate volume of reconstituted drug product solution based on the subject's dose and body weight will be withdrawn and the teprotumumab reconstituted drug product solution will be diluted with normal saline (0.9% NaCl) in the infusion bag.

The infusion rate may be reduced and the dose may be interrupted or held based on tolerability. The first and second infusions will be administered over approximately 90 minutes (but not less than 80 minutes). Subsequent infusions will be administered over approximately 60 minutes (but not less than 50 minutes) providing there are no significant infusion-associated events.

3.8. STUDY PROCEDURES AND FLOWCHART

The Schedule of Assessments is presented in [Table 1](#) below.

Table 1: Schedule of Assessments

Study Visit	Open-Label Treatment Period ¹ (24 Weeks)											Follow-Up Period ² (24 weeks)			Follow-Up Contact ³ (48 Weeks)			
	1	2	3	4	5	6	7	8	9	10	11/ PW ⁴	FU1	FU2	FU3/ PW ⁵	FU4	FU5	FU4	FU5
Week (W)/ Month (M)	Day 1 ⁶	W1	W3	W4/ M1	W6	W9	W12/ M3	W15	W18	W21	W24/ M6	W28/ M7	W36/ M9	W48/ M12	W48/ M12	W72/ M18	W72/ M18	W96/ M24
Visit Window (± days)	(+14) ⁷	(±1)	(±3)	(±1)	(±3)	(±3)	(±3)	(±3)	(±3)	(±3)	(±7)	(±7)	(±7)	(±7)	(±14)	(±14)	(±14)	(±14)
Subject response in Study HZNP-TEP-301	Proptosis Non-responder or Relapse											Proptosis Non-responder Only			Relapse Only		Proptosis Non-responder Only	
Informed Consent	X																	
Review inc/exc criteria	X																	
Weight ⁸	X ⁹						X				X		X	X				
Study drug infusion ¹⁰	X		X		X	X	X	X	X	X								
Phone (email) contact for safety 24 hours postdose ¹¹	X		X															
Investigator assessment of active disease	X				X		X		X		X	X	X	X				
Efficacy assessments																		
CAS	X ⁹				X		X		X		X	X	X	X				
Clinical Measures of Severity - includes proptosis, diplopia, and motility restriction	X ⁹				X		X		X		X	X	X	X				
Safety assessments																		
Pregnancy Test ¹²	X ⁹		X		X	X	X	X	X	X	X	X	X	X				

Study Visit	Open-Label Treatment Period ¹ (24 Weeks)											Follow-Up Period ² (24 weeks)			Follow-Up Contact ³ (48 Weeks)			
	1	2	3	4	5	6	7	8	9	10	11/ PW ⁴	FU1	FU2	FU3/ PW ⁵	FU4	FU5	FU4	FU5
Week (W)/ Month (M)	Day 1 ⁶	W1	W3	W4/ M1	W6	W9	W12/ M3	W15	W18	W21	W24/ M6	W28/ M7	W36/ M9	W48/ M12	W48/ M12	W72/ M18	W72/ M18	W96/ M24
Visit Window (± days)	(+14) ⁷	(±1)	(±3)	(±1)	(±3)	(±3)	(±3)	(±3)	(±3)	(±3)	(±7)	(±7)	(±7)	(±7)	(±14)	(±14)	(±14)	(±14)
Physical exam ¹³	X ^{9,13}	X			X		X		X		X ¹³			X ¹³				
Ophthalmic exam ¹⁴	X ⁹	X			X		X		X		X			X				
Vital Signs ¹⁵	X ⁹	X	X	X	X	X	X	X	X	X	X	X	X	X				
12-Lead ECG	X ⁹		X		X		X				X			X				
Clinical laboratory tests ¹⁶																		
Chemistry (excl. glucose)	X ^{9,17}		X		X	X	X		X		X		X	X				
Thyroid (FT3, FT4, TSH) ¹⁸	X ⁹		X		X	X	X		X		X		X	X				
Hematology	X ⁹	X	X	X	X	X	X	X	X	X	X		X	X				
Glucose ¹⁹	X ⁹	X	X	X	X	X	X	X	X	X	X		X	X				
HbA1c	X ⁹						X				X		X	X				
Urinalysis	X ⁹		X		X	X	X		X		X		X	X				
ADA/NAb samples ²⁰	X ⁹		X			X					X ²¹		X	X				
AE, SAE assessment ²²	X ⁹	X	X	X	X	X	X	X	X	X	X	X	X	X				
Concomitant medications	X ⁹	X	X	X	X	X	X	X	X	X	X	X	X	X				
GO-QoL Questionnaire	X ⁹				X		X				X	X		X				
PK samples ²³	X	X	X	X		X					X ²¹							
Contact (phone/email) to assess additional TED treatment ²⁴															X	X	X	X

ADA=anti-drug antibody; AE=adverse event; CAS=Clinical Activity Score; ECG=electrocardiogram; FT3=free triiodothyronine; FT4=free thyroxine; FU=Follow-Up; GO-QoL=Graves' Ophthalmopathy Quality of Life Questionnaire; HbA1c=glycated hemoglobin; M=month; NAb=neutralizing antibody; PK=pharmacokinetic; PW=premature withdrawal; SAE=serious adverse event; TED=thyroid eye disease; TSH=thyroid stimulating hormone; W=week.

Footnotes:

1. Open-label Treatment Period. Subjects with TED who are proptosis non-responders at Week 24 of HZNP-TEP-301 or were proptosis responders at Week 24 but who meet criteria for re-treatment due to relapse during the Follow-Up Period in HZNP-TEP-301 are eligible to enroll and receive 8 infusions of teprotumumab (10 mg/kg for the first infusion titrated to 20 mg/kg for the remaining infusions) in an open-label fashion.
2. Proptosis non-responders from Study HZNP-TEP-301 will participate in a 6-month Follow-Up Period; subjects who relapsed during the Follow-Up Period of HZNP-TEP-301 will not participate.
3. Proptosis non-responders from Study HZNP-TEP-301 who complete the Month 12 Visit and subjects who relapsed during the Follow-Up Period of HZNP-TEP-301 and complete the Week 24 Visit will be contacted via phone or email by research staff to enquire if any treatment for TED has been received since last study contact.
4. If subjects wish to discontinue study drug during the open-label Treatment Period, subjects will return for a clinic visit and undergo the Week 24 assessments, except for PK and ADA evaluations. Subjects who were proptosis non-responders at Week 24 of HZNP-TEP-301 will be encouraged to continue study participation in the Follow-Up Period.
5. If a subject wishes to prematurely discontinue from the study during the Follow-Up Period, he/she will return for a clinic visit and undergo the Month 12 assessments prior to discharge.
6. On Day 1 (Baseline), subjects will receive the first dose of study drug; however, Baseline assessments will be performed prior to dosing.
7. Day 1 will occur within 14 days after the final visit of Study HZNP-TEP-301 (Week 24 for proptosis non-responders and up to Week 72 for subjects who relapse).
8. Dosing will be adjusted if there is a change in weight during the Treatment Period. The weight obtained at Week 12 can be used in dose calculations beginning at Week 12 or Week 15.
9. If Day 1 of the extension study occurs on the same day as the final visit of HZNP-TEP-301 (Week 24 [or PW1] for proptosis non-responders and Week 72 [or PW2] for subjects who relapse), assessments do not need to be repeated, and the final assessments from the lead-in study will serve as the Baseline assessments for the extension study.
10. Subjects will receive teprotumumab 10 mg/kg on Day 1 followed by 20 mg/kg q3W for the remaining 7 infusions.
11. Phone (or email) contact by research staff focusing on safety and tolerability aspects will be made the day after infusion for the first and second infusions, and thereafter as deemed appropriate. In addition, subjects who experience an infusion-associated event after any subsequent infusion will also be contacted by phone (or email) by research staff the day after the infusion, and thereafter as deemed appropriate.
12. Perform urine pregnancy tests prior to dose (as applicable) for female subjects of childbearing potential (including those with an onset of menopause <2 years prior to Baseline of HZNP-TEP-302, non-therapy-induced amenorrhea for <12 months prior to Baseline of HZNP-TEP-302, or not surgically sterile [absence of ovaries and/or uterus]).
13. Physical exam will include assessment of presence or absence of pretibial myxedema on Day 1 and Week 24/PW of the Treatment Period and Month 12/PW of the Follow-Up Period. If present, measurements of instep and calf will be taken.
14. Ophthalmic exam: best corrected visual acuity, pupil exam, color vision assessment, Ishihara color plates (or equivalent) or related red desaturation, intraocular pressure, and slit lamp exam. If significant abnormalities are noted compared to previous visits, including a loss of 2 lines or more of vision, development of pupil abnormalities

including APD, rise in intraocular pressure, development of corneal infiltrates or other abnormalities not here specified but of concern to the ophthalmologist, further investigations of visual function will be conducted according to the ophthalmologist decision.

15. Vital signs (heart rate, blood pressure, respiratory rate, temperature) will be measured at all clinic visits. Vital signs will be measured pre- and post-infusion on Day 1 and Week 3, and pre-dose on all other infusion days. Additional vital signs will be monitored if infusion-associated AEs occur.
16. Non-diabetic subjects should be fasting at Weeks 1 and 4 only. Diabetic subjects should be fasting at each visit blood glucose is evaluated.
17. ALT/AST must be ≤ 3 x the upper limit of normal (ULN) and serum creatinine must be < 1.5 x the ULN (according to age) at the most recent clinic visit to be eligible for enrollment.
18. Subjects must be euthyroid with the baseline disease under control or have mild hypo- or hyperthyroidism (defined as free thyroxine [FT4] and free triiodothyronine [FT3] levels $< 50\%$ above or below the normal limits) at the most recent clinic visit. Every effort should be made to correct the mild hypo- or hyperthyroidism promptly and to maintain the euthyroid state for the full duration of the clinical trial.
19. HbA1c must be $< 9.0\%$ at the most recent clinic visit. If the HbA1c is elevated and considered clinically significant at any time point after Baseline, it will be repeated approximately every 45 days until it returns to normal or the baseline value.
20. If a sample is positive in the ADA test, after confirmatory and reactive titer testing, the sample will then be tested for NAb. If the subject tests positive for NAb, he/she will be followed until levels either revert to Baseline or the subject's value decreases or remains stable. Any subject with a positive NAb test at Week 48 (or PW) during the Follow-Up Period will continue to be followed until the subject's value decreases or remains stable.
21. Not collected for subjects who prematurely discontinue from the open-label Treatment Period.
22. Adverse events that are ongoing at completion of HZNP-TEP-301 and/or occur prior to dosing on Day 1 will be considered pre-dose AEs. Adverse events occurring or worsening after the dose on Day 1 through the end of the Treatment Period will be considered treatment-emergent AEs (TEAEs). Adverse events occurring or worsening during the Follow-Up Period will be considered postdose AEs. All SAEs that occur from the signing of informed consent through 30 days after study discontinuation will be recorded.
23. PK samples will be collected prior to, and at the end of, the infusion on Day 1 and Weeks 3 and 9 of the open-label Treatment Period; additional single samples will be collected at Weeks 1, 4, and 24.
24. If TED treatment has been received since last contact, the subject will be questioned regarding type of treatment and outcome/response.

4. ENDPOINTS

4.1. PRIMARY EFFICACY ENDPOINT

The primary efficacy endpoint is the proptosis responder rate (percentage of subjects with a ≥ 2 mm reduction from Baseline in proptosis in the study eye, without deterioration [≥ 2 mm increase] of proptosis in the fellow eye) at Week 24.

Baseline refers to Study Baseline defined in Section [6.2.3](#).

4.2. SECONDARY EFFICACY ENDPOINTS

The secondary endpoints are the following:

1. Percentage of subjects with a CAS value of 0 or 1 in the study eye at Week 24.
2. Mean change from Study Baseline to Week 24 in proptosis measurement in the study eye.
3. Diplopia responder rate (percentage of subjects with Study Baseline diplopia >0 in study eye who have a reduction from Study Baseline of ≥ 1 grade with no corresponding deterioration [≥ 1 grade worsening] in the fellow eye) at Week 24.
4. Mean change from Study Baseline to Week 24 in the GO-QoL questionnaire overall score.

4.3. EXPLORATORY EFFICACY ENDPOINTS

Exploratory efficacy endpoints include:

1. The overall responder rate (percentage of subjects with ≥ 2 -point reduction in CAS AND ≥ 2 mm reduction in proptosis from Study Baseline, provided there is no corresponding deterioration [≥ 2 point/mm increase] in CAS or proptosis in the fellow eye) at Week 24.
2. Clinical Measures of Severity individual response status frequencies and percentage of responders for each component of clinical severity at Week 24.
3. Mean change from Study Baseline to Week 24 in the CAS.
4. Overall responder rate at Week 24 stratified by the level of response (high responders, responders, low responders, and non-responders; see Section 8.3.4 for definitions).
5. Mean change from Study Baseline to Week 24 in the GO-QoL questionnaire VF and A subscale scores.
6. Mean change from Study Baseline to Week 24 on the motility component of the Clinical Measures of Severity.

4.4. EXPLORATORY PHARMACOKINETIC ENDPOINTS

The PK endpoints covered in the scope of this SAP include:

- Descriptive summaries of serum concentrations by time point
- Listing of serum concentrations by time point

4.5. SAFETY ENDPOINTS

Safety endpoints include the following:

- Adverse events (AE), including AE of special interest (AESI)
- Concomitant medication
- Descriptive summary of immunogenicity
- Physical examination
- Ophthalmic examination
- Vital signs
- Clinical laboratory assessments (complete blood count, chemistry [including thyroid panel and HbA1C], and urinalysis)
- Pregnancy testing
- Electrocardiogram (ECG)

5. ANALYSIS POPULATIONS

5.1. INTENT-TO-TREAT POPULATION

The Intent-to-Treat (ITT) Population will include all subjects who are enrolled (signed informed consent) in the study. Subjects will be analyzed according to treatment received in HZNP-TEP-301 study. The ITT Population will be used for all analyses of efficacy and safety endpoints.

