#### Muscle Spasms

During the TED01RV study, muscle spasms were identified in 19% of the subjects receiving teprotumumab versus 5% of those receiving placebo. In the teprotumumab group, 8 subjects had muscle spasms (6 had Grade 1 and 2 had Grade 2); only 2 subjects experienced the event for longer than one week and were treated with muscle relaxants. If possible, avoid medications

known to cause muscle spasms or muscle toxicity such as diuretics or statins and evaluate for other causes of muscle spasm such as electrolyte abnormalities and dehydration.

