#### **9.5.6 Study Procedures**

Subjects who provide informed consent and who meet all the entry criteria for participation in this study will be enrolled in the open-label extension study.

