## **9.6 Statistical Methods and Determination of Sample Size**

Detailed statistical analyses will be presented in a separate statistical analysis plan (SAP), and analyses presented in the SAP will supersede those presented in the protocol. Some key points identified for statistical analyses are outlined below.

The primary analyses will be conducted on the Intent-to-Treat (ITT) population. All efficacy and safety endpoints will be summarized using descriptive statistics and/or number and percentage of subjects, and will be stratified by the treatment received in HZNP-TEP-301 as well as overall.

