### **9.6.2 Populations for Analysis**

The following analysis populations will be defined for this study:

- Intent-to-Treat (ITT)
- Safety Population

The ITT population will include all subjects who are enrolled in the study. Full details of the analysis populations will be described in the SAP.

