#### **9.6.3.4 Safety Analyses**

The safety analysis population will include all subjects who receive at least one dose and had at least one post-dose safety assessment. All safety parameters will be summarized and presented in tables based on this safety population. Details of the safety data analysis will be presented in the SAP.

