7. DEMOGRAPHIC, OTHER BASELINE CHARACTERISTICS, MEDICATION AND PROTOCOL DEVIATIONS

7.1. SUBJECT DISPOSITION AND DISCONTINUATION

A summary of subject disposition will be provided including the number of subjects screened and the number and percent of screen failures. Further, the number and percent of subjects enrolled overall and by subject enrollment type (proptosis non-responders in HZNP-TEP-301 and subjects who relapsed during the Follow-Up Period of HZNP-TEP-301) will be provided, as well as the number of subjects in each analysis population (ITT and PK Population). In addition, the number and percent of subjects in each of the following categories will be provided:

- Completed the Treatment Period
- Discontinued early from the Treatment Period
 - Proptosis non-responder in HZNP-TEP-301 and did not continue in the Follow-Up Period with reasons for discontinuations
 - Proptosis non-responder in HZNP-TEP-301 and continued in Follow-Up Period with reasons for discontinuation Subjects who relapsed in HZNP-TEP-301
- Had any data collected during the Follow-Up Period
- Completed the study
 - Completed the Treatment Period and Follow-Up Period for subjects who were proptosis non-responders in HZNP-TEP-301
 - Discontinued from the Treatment Period but completed the Follow-up Period for subjects who were proptosis non-responders in HZNP-TEP-301
 - Completed the Treatment Period for subjects who relapsed during the Follow-Up Period of HZNP-TEP-301
- Discontinued early from the study by reason for discontinuation (Did not complete the Treatment Period and did not continue in the Follow-Up Period for subjects who were proptosis non-responders in HZNP-TEP-301; did not complete the Treatment Period, continued in the Follow-Up Period, but did not complete the Follow-Up Period for subjects who were proptosis non-responders in HZNP-TEP-301; completed the Treatment Period and did not continue in the Follow-Up Period for subjects who were proptosis non-responders in HZNP-TEP-301; completed the Treatment Period, continued in the Follow-Up Period but did not complete the Follow-Up Period for subjects who were proptosis non-responders in HZNP-TEP-

301; did not complete the Treatment Period for subjects who relapsed during the Follow-Up Period of HZNP-TEP-301)

- o Reasons for discontinuation

Percentages will be based on the number of subjects in the ITT Population.

Subject disposition information will be summarized by treatment received in HZNP-TEP-301 and overall.

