In addition, a separate analysis will be provided for time to proptosis response. Time to proptosis response will be measured as the days from the first dose date to the earliest visit date in which the criteria are met for proptosis response (≥ 2 mm reduction from Study Baseline in proptosis in the study eye, without deterioration [≥ 2 mm increase] of proptosis in the fellow eye) within the Treatment Period, calculated as:

first visit date in which criteria for proptosis response are met - first dose date + 1

Subjects not achieving a proptosis response within the Treatment Period will be censored at their last visit date with a proptosis assessment within the Treatment Period. Kaplan-Meier estimates will be provided by treatment received in HZNP-TEP-301 of the 25th percentile, median, and 75th percentile. 95% confidence intervals (CI) will be provided for the median. Analyses will be based on the ITT Population. Any ITT subject who is enrolled but not dosed will be censored at Day 0.

The analysis will be repeated for the fellow eye (using a definition analogous to the one used for the study eye).

Plots of the time to proptosis response will be provided by treatment received in HZNP-TEP-301 for the study eye and fellow eye.

Further, for subjects who were proptosis non-responders in HZNP-TEP-301, sustained proptosis response at a given visit in the HZNP-TEP-302 Follow-Up Period will be defined for HZNP-TEP-302 Week 24 proptosis responders as:

- ≥ 2 mm reduction from Baseline in proptosis in the study eye, without deterioration (≥ 2 mm increase) of proptosis in the fellow eye, AND
- No additional TED treatment received by the time of the visit.

Additional TED treatment will include any instances of TED medication (identified by manual listing review), TED concomitant procedures (identified by manual listing review), TED surgical procedures, and/or orbital radiation treatments.

At each assessment after Week 24, the proportion of subjects who are sustained responders will be summarized by treatment received in HZNP-TEP-301. Subjects who are missing proptosis values at a visit will be considered non-responders at that visit.

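### The SAP puts safety percentages on an ITT set defined by signed consent, so any undosed subject would lower every Treatment Period TEAE and AESI rate

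*SAP*

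**What the plan says.** **Who is enrolled.** Protocol 9.5.6: "Subjects who provide informed consent and who meet all the entry criteria for participation in this study will be enrolled". Protocol 9.6.2: "The ITT population will include all subjects who are enrolled in the study". SAP 5.1 keeps the link between enrolment and ITT but adds a gloss: "The Intent-to-Treat (ITT) Population will include all subjects who are enrolled (signed informed consent) in the study". It sets no dosing condition. SAP 7.1 plans to report "the number of subjects screened and the number and percent of screen failures", and lists enrolled subjects and the analysis populations as further items.

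**Which set carries safety.** Protocol 9.6.3.4: "The safety analysis population will include all subjects who receive at least one dose and had at least one post-dose safety assessment". SAP 5.1 and SAP 10 use ITT instead. SAP 12 declares the change and gives as its reason that the two populations are expected to coincide. Protocol 9.6 allows this, since "analyses presented in the SAP will supersede those presented in the protocol".

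**Undosed subjects.** For the time-to-response analysis, SAP 8.1 says: "Any ITT subject who is enrolled but not dosed will be censored at Day 0". SAP 10 has no matching rule.

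**Denominators.** SAP 10.3 names one for Follow-Up Period AEs (subjects entering that period) and none for Treatment Period TEAEs or AESIs. The index in SAP 16 labels the Treatment Period tables ITT, and SAP 14.2.4 puts the analysis-set N in the column heading. SAP 14.2.5.2 defaults to subjects in the analysis set with an observation and requires a footnote identifying the denominator.

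**The concern.** Two choices combine. The consent gloss widens ITT beyond the protocol's enrolled set; taken literally, it could admit someone who signs consent and then fails an entry criterion. That wider set then replaces a safety set that required dosing. A subject who signs but is never infused counts in N, yet by the TEAE definition in SAP 10.3 has no period in which an event could qualify.

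At stake are the TEAE and AESI percentages (hyperglycemia, muscle spasm, hearing loss and the others). Any dilution makes the drug look safer, which is the wrong direction for a safety summary. It is largest in the columns split by HZNP-TEP-301 treatment, where N is smallest. Shift tables are not affected in this way, because SAP 10.5, 10.6, 10.8 and 10.10 base those percentages on subjects with both a baseline and a post-baseline value.

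**Working it through.** The plan states no figure for this point, so there is nothing to reproduce. The check is a reading of the rules followed by simple arithmetic.

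**Step 1: which denominator applies.** SAP 5.1 and SAP 10 assign safety to ITT, SAP 16 labels the TEAE and AESI tables ITT, and SAP 14.2.4 heads columns with the analysis-set N. Together these make ITT the Treatment Period denominator. The default in SAP 14.2.5.2 adds no dosing condition, and having an observation has no clear meaning for AE incidence.

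**Step 2: can an undosed ITT subject exist?** Protocol 9.5.6.1 puts consent before all other Day 1 procedures and then requires eligibility review and, where applicable, a negative pregnancy test before treatment. Protocol section 11 requires an eCRF for everyone who signs. SAP 8.1 has a rule for such a subject. So it is possible. Because consent and first infusion are both scheduled for Day 1 (Protocol 2.1), it should be uncommon.

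**Step 3: numerator.** Under SAP 10.3 the TEAE period opens at the first HZNP-TEP-302 dose, so an undosed subject contributes no TEAE. One rare exception is that SAP 6.3.4 treats an AE with a wholly missing start date as treatment-emergent unless its stop date rules that out.

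**Step 4: size.** Let r be the rate among dosed subjects, D the number dosed and U the number undosed.

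- Reported rate = r × D/(D+U)
- Relative fall = U/(D+U)

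The reference rate is muscle spasm in the earlier TED trial: 8/43 = 18.6% (Protocol Table 7.2). The text of Protocol 7.1.3.4.5.5.1 rounds it: "muscle spasms were identified in 19% of the subjects receiving teprotumumab versus 5% of those receiving placebo". It is used only to give the formula a scale. SAP 3.5 gives no sample size, so **D and U are assumed**. D = 15 stands for one HZNP-TEP-301 treatment column.

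| D | U = 0 | U = 1 | U = 2 |
|---|---|---|---|
| 60 | 18.6% | 18.6 × 60/61 = 18.3% | 18.6 × 60/62 = 18.0% |
| 40 | 18.6% | 18.6 × 40/41 = 18.2% | 18.6 × 40/42 = 17.7% |
| 15 | 18.6% | 18.6 × 15/16 = 17.4% | 18.6 × 15/17 = 16.4% |

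(Computed with the unrounded 8/43.)

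**Step 5: when the relative fall reaches 5%.**

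- D = 60 needs U = 4: 4/64 = 6.25%, whereas 3/63 = 4.8%.
- D = 40 needs U = 3: 3/43 = 7.0%, whereas 2/42 = 4.8%.
- D = 15 needs U = 1: 1/16 = 6.25%.

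**The case against.** The sponsor has a good defence. The population change is declared with a reason in SAP 12, and the protocol lets the SAP prevail. The expectation behind it may have been informed: SAP 2.2 reports that disposition and exposure data from this study had already gone into the integrated safety summary and its 120-day update. The Day 0 rule in SAP 8.1 may be defensive programming, since a time measured from first dose needs some convention for a subject without one. SAP 7.1 keeps screen failures apart from enrolled subjects, so the consent gloss may be loose wording. Footnotes must identify each denominator, and the mock-ups are in a separate file that is not available here. Undosed subjects would be visible in the dose-count summary of SAP 10.1 and in the listings.

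Most of this stands, and it rules out three stronger readings that a reader might infer. First, the denominator is not undefined: the SAP, read as a whole, makes it ITT. Second, this is not an undisclosed departure from the protocol. Third, nothing shows that reported rates will in fact be too low, because no passage indicates that U exceeds zero.

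What the defence does not supply is a rule for the case where the expectation fails. A footnote identifies a denominator but does not correct it. SAP 12 also does not list the change in the meaning of enrolment.

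**Conclusion.** The point holds as a minor one. As written, the SAP lowers every Treatment Period TEAE and AESI percentage by the factor D/(D+U) whenever an undosed subject is in ITT. The effect is zero if all ITT subjects are dosed, which is what SAP 12 expects. With one undosed subject, the illustrative rate falls by 0.3 to 0.4 percentage points at D = 60 or 40 (18.60 to 18.30, and 18.60 to 18.15), and by 1.2 points at D = 15 (18.6 to 17.4). These sizes rest on assumed D and U and a borrowed reference rate.

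Confidence is high in the textual mismatch and in the direction of the effect. The documents do not settle whether the effect will occur. It would not be right to extend the criticism to the primary responder rate or the other efficacy summaries: keeping undosed enrolled subjects in ITT for efficacy is a separate choice and is not questioned here.

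**What to change.** 1. In SAP 5.1, replace the parenthesis about consent with the rule in Protocol 9.5.6 (consented and met all entry criteria), and state that screen failures are not in ITT.
2. In SAP 10.3, state that Treatment Period TEAE and AESI percentages are based on subjects with at least one HZNP-TEP-302 dose, just as Follow-Up Period AEs already have their own denominator. Restoring the protocol's Safety Population would serve nearly the same end, but it also requires a safety assessment after dosing, so the two sets could differ; the SAP should name one.
3. Keep the dose-count table in SAP 10.1 on ITT, so that anyone with zero doses stays visible.
4. Leave efficacy on ITT.
5. Record the change in SAP 12.

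The cost is a few sentences and one population flag. No new data, extra tables or sensitivity summary are needed. If every ITT subject proves to have been dosed, the TEAE and AESI percentages are unchanged.
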